APPENDIX VI: PATIENT GLOBAL IMPRESSION OF SEVERITY (PGIS) EXAMPLE

Please choose the response below that best describes the severity of your Psoriasis SYMPTOM / OVERALL STATUS over the [REDACTED]

- None
- Mild
- Moderate
- Severe

APPENDIX VII: PATIENT GLOBAL IMPRESSION OF CHANGE (PGIC) EXAMPLE

Please choose the response below that best describes the overall change in your psoriasis since you started taking the study medication:
 
Please check  one box only
	
	Much better
	A little better
	No Change
	A little worse
	Much Worse

APPENDIX VIII: ITCH NUMERIC RATING SCALE (ITCH NRS) EXAMPLE

Please rate the itching severity due to your psoriasis by circling the number that best describes your **worst** level of itching in the [redacted].

For subjects with scalp psoriasis:

Please rate the itching severity of your **scalp** due to your psoriasis by circling the number that best describes your **worst** level of itching in the _____.

APPENDIX IX: HEALTH ASSESSMENT QUESTIONNAIRE OF DISABILITY (HAQ-DI) EXAMPLE

Please check the box which best describes your abilities over the past week:

DRESSING & GROOMING

Are you able to:

	Without ANY difficulty	With SOME difficulty	with MUCH difficulty	UNABLE to do
Dress yourself, including shoelaces and buttons?				
				

Shampoo your hair?

Check if you usually need help from another person

Check if you usually use button hook, zipper pull, shoe horn, etc.

ARISING

Are you able to:

Stand up from a straight chair?	Without ANY difficulty	With SOME difficulty	with MUCH difficulty	UNABLE to do
				
Get in and out of bed?				

Check if you usually need help from another person

Check if you usually use special or built up chair

EATING

Are you able to:

Cut your own meat?	Without ANY difficulty	With SOME difficulty	with MUCH difficulty	UNABLE to do
				
Lift a full cup or glass to your mouth?				
Open a new milk carton?				

Check if you usually need help from another person

Check if you usually use built up or special utensils

WALKING

Are you able to:

Walk outdoors on flat ground?	Without ANY difficulty	With SOME difficulty	with MUCH difficulty	UNABLE to do
				
Climb up five steps?				

Check if you usually need help from another person

Check if you usually use cane, walker, crutches, wheelchair

HYGIENE

Are you able to:

Wash and dry your body?

Without ANY difficulty	With SOME difficulty	with MUCH difficulty	UNABLE to do
------------------------------	-------------------------	-------------------------	-----------------

			
--------------------------	--------------------------	--------------------------	--------------------------

Take a tub bath?

			
--------------------------	--------------------------	--------------------------	--------------------------

Get on and off the toilet?

			
--------------------------	--------------------------	--------------------------	--------------------------

Check if you usually need help from another person

Check if you usually use bathtub bar, long-handled appliances in bathroom, raised toilet seat

REACH

Are you able to:

Reach and get down a 5 pound object (such as a bag of sugar) from above your head?

Without ANY difficulty	With SOME difficulty	with MUCH difficulty	UNABLE to do
------------------------------	-------------------------	-------------------------	-----------------

			
--------------------------	--------------------------	--------------------------	--------------------------

Bend down to pick up clothing from the floor?

			
--------------------------	--------------------------	--------------------------	--------------------------

Check if you usually need help from another person

Check if you usually use long-handled appliances for reach

GRIP

Are you able to:

Open car doors?

Without ANY difficulty	With SOME difficulty	with MUCH difficulty	UNABLE to do
------------------------------	-------------------------	-------------------------	-----------------

			
--------------------------	--------------------------	--------------------------	--------------------------

Open previously opened jars?

			
--------------------------	--------------------------	--------------------------	--------------------------

Turn faucets on and off?

			
--------------------------	--------------------------	--------------------------	--------------------------

Check if you usually need help from another person

Check if you usually use jar opener for jars previously opened

ACTIVITIES

Are you able to:

Run errands and shop?

Without ANY difficulty	With SOME difficulty	with MUCH difficulty	UNABLE to do
------------------------------	-------------------------	-------------------------	-----------------

			
--------------------------	--------------------------	--------------------------	--------------------------

Get in and out of a car?

Do chores such as vacuuming or yard work?

Check if you usually need help from another person to do errands and chores

To be completed by the clinic staff:

HAQ-DI Score: _____

HAQ-DI Scoring

There are four possible responses for the Disability Index questions:

If more than 2 of the categories, or 25%, are missing, the scale is not scored.

There are 3 steps to scoring the HAQ:

1. For each section the score given to that section is the worst score within the section, i.e. if one question is scored 1 and another 2, then the score for the section is 2.
 - Without ANY difficulty = 0
 - With SOME difficulty = 1
 - With MUCH difficulty = 2
 - UNABLE to do =3
2. In addition, if an aide or device is used or if help is required from another individual, then the minimum score for that section is 2. If the section score is already 2 or more then no modification is made.
 - No assistance is needed, add '0'
 - A special device is used by the patient in his/her usual activities, minimum score is '2'
 - The patient usually needs help from another person, minimum score is '2'
 - The patient usually needs BOTH a special device AND help from another person, the section score is '3'
3. Divide the final sum by the number of categories answered. The score for the disability index is the mean of the 8 category scores rounded to the nearest value. If 1 or 2 of the categories are missing, the sum of the categories is divided by the number of answered categories.

Some patients may question whether their response should reflect a particularly good or bad time, which is out of the time frame requested, because they feel that their response may be missing those times when their functional ability changes. The study requires repeating the HAQ at specific and regular time intervals to examine patterns of function. Inquiring about these activities only when patients are feeling particularly good or bad would result in inaccurate and biased data. The score is not modified if they have difficulties sometimes or required help only occasionally.

Addressing some scenarios which occasionally arise:

- If an item does not apply to an individual, e.g., they do not shampoo their hair, take tub baths, or reach for a heavy object above their heads, then they should leave the item(s) blank since the purpose is to obtain data about what they can do.
- If a patient uses adapted or modified aids or devices (e.g., clothing, faucets, cars), then they should answer the questions based on their usual equipment. If they have no difficulty using the adapted equipment, then they would mark the “no difficulty” column. The adapted equipment (aids and devices) will be taken into account in the assistance variables (see below).
- If an individual can open their own door but not for others, then they should respond in consideration of their own requirements.

APPENDIX X: PATIENT GLOBAL ASSESSMENT OF DISEASE ACTIVITY (PtGA) EXAMPLE

Note: please ensure that the line is 100 mm in length after printing the source document and measuring the distance

Considering all the ways your arthritis affects you, how are you feeling TODAY?" Please answer by placing a mark on the line below:

To be completed by the clinic staff:

VAS Score: _____ / 100

APPENDIX XI: PATIENT ASSESSMENT OF PAIN (PtA-P) EXAMPLE

Note: please ensure that the line is 100 mm in length after printing the source document and measuring the distance

How much pain due to your arthritis are you currently experiencing?

Please rate your pain by placing a mark on the line corresponding to your CURRENT level of pain.

To be completed by the clinic staff:

VAS Pain: _____ / 100

APPENDIX XII: TENDER AND SWOLLEN JOINT COUNT EXAMPLE

To allow for sufficient joint inspection, the physician should ask the patient to wear a standard gown and sit on the front end of the examination table.

In PsA, joint swelling and tenderness are caused by inflammation of the joint synovium, increased synovial fluid production, and periarticular swelling in the joint capsule and surrounding tissues. Visual clues of joint swelling include enlargement of the joint soft tissue, skin stretching with loss of folds and furrows, and red or blue skin color changes around the joint.

After inspection, each joint is examined by palpation using the thumbs and index fingers. Joint swelling may be detected by finding tissue sponginess and ballotting the joint for increased synovial fluid. Identifying anatomical landmarks of specific joints and comparing joints on one side of the body with those on the other side are helpful in assessment of joint swelling.

[figure not shown]
[figure not shown]
Note that PsA joint and soft tissue structural abnormalities may cause joint malalignment, which may influence the assessment for swelling. Muscles and subcutaneous tissue can atrophy, making the joints appear more prominent. Adipose tissue may be present near joints and is related, in part, to body size; it should not be confused with inflammation. Joints that have severe deformity or are fused should be noted and should not be included in the scoring for swelling.

During joint palpation, tenderness is determined primarily by applying sufficient pressure to the joint line to cause blanching of the examiner's fingernail bed. The patient is asked, "Is that tender?"

Joint tenderness also is assessed by moving joints through their respective ranges of motion. Limited range of motion may be a sign of joint inflammation; this should be interpreted in the context of simultaneous assessment of a patient's pain reaction to joint movement, such as facial grimacing or joint withdrawal.

Joint Count Scoring Sheet

Tender and swollen measurements

Tender Joints: Number ____ /68

Swollen Joints: Number ____ /66

APPENDIX XIII: PHYSICIAN'S GLOBAL ASSESSMENT OF DISEASE ACTIVITY (PGA) EXAMPLE

[figure not shown]
Note: please ensure that the line is 100 mm in length after printing the source document and measuring the distance

[figure not shown]
How do you assess your patient's current arthritis?

[figure not shown]

[figure not shown]
To be completed by the clinic staff:

[figure not shown]
VAS Score: _____ / 100

[figure not shown]

	 		
	                                        <img alt="Redacted content" data-bbox="195 718

## LIST OF ABBREVIATIONS

Abbreviation	Explanation
ACLS	Advanced Cardiac Life Support
ACR	American College of Rheumatology
AE	Adverse Event
ALC	Absolute Lymphocyte Counts
ALT	Alanine Aminotransferase
ANC	Absolute Neutrophil Count
aPTT	Activated Partial Thromboplastin Time
AST	Aspartate Aminotransferase
BMI	Body Mass Index
BSA	Body Surface Area
CASPAR	Classification Criteria for Psoriatic Arthritis
COPD	Chronic Obstructive Pulmonary Disease
COVID-19	Coronavirus Disease-2019
CRA	Clinical Research Associate
CRO	Contract Research Organization
CRP	C-Reactive Protein
CV	Coefficient of Variation
DLQI	Dermatology Life Quality Index
DSMB	Data Safety Monitoring Board
ECG	Electrocardiogram
eCRF	Electronic Case Report Form
EOT	End of Treatment
FEV	Forced Expiratory Volume
FVC	Forced Vital Capacity
GGT	Gamma Glutamyltransferase
HAQ-DI	Health Assessment Questionnaire of Disability
HBsAg	Surface Antigen of The Hepatitis B Virus (HBV)
hCG	Human Chorionic Gonadotropin
HCV	Hepatitis C Virus
HDL	High-Density Lipoproteins
HEENT	Head, Eyes, Ears, Nose and Throat
HIV	Human Immunodeficiency Virus
IA	Interim Analysis
IGA	Investigator's Global Assessment
INR	International Normalized Ratio
ITT	Intent to Treat
LDL	Low-Density Lipoprotein
MCV	Mean Corpuscular Volume
MedDRA	Medical Dictionary for Regulatory Activities
MM	Medical Monitor
mNAPSI	Modified Nail Psoriasis Severity Index

NRS	Numeric Rating Scale
OCT	Optical Coherence Tomography
PASI	Psoriasis Area and Severity Index
PD	Pharmacodynamic
PGA	Physician's Global Assessment
PGIC	Patient Global Impression of Change
PGIS	Patient Global Impression of Severity
PK	Pharmacokinetics
PML	Progressive Multifocal Leukoencephalopathy
PP	Per Protocol
PPGA	Palmoplantar Physician Global Assessment
PRES	Posterior Reversible Encephalopathy Syndrome
PsA	Psoriatic Arthritis
PSSD	Psoriasis Symptoms And Signs Diary
PT	Prothrombin Time
PtAP	Patient Assessment of Pain
PtGA	Patient Global Assessment of Disease Activity
QTcF	QT Corrected by Fridericia's Formula
RF	Rheumatoid Factor
S1P	Sphingosine-1-Phosphate
SAP	Statistical Analysis Plan
SUSAR	Suspected Unexpected Serious Adverse Reactions
TEAE	Treatment Emergent Adverse Event
VAS	Visual Analogue Scale
VZV	Varicella Zoster Virus
WBC	White Blood Cells

## 1. INTRODUCTION

The purpose of this statistical analysis plan (SAP) is to provide details of the statistical analyses that have been outlined within the protocol "A Randomized, Double-Blind, Placebo-Controlled Study to Assess the Efficacy and Safety of SCD-044 in the Treatment of Moderate to Severe Plaque Psoriasis", version 4.1, dated July 28, 2023.

Sun Pharmaceutical Industries Ltd. is developing a Sphingosine 1-phosphate (S1P) receptor agonist, SCD-044 to treat moderate to severe plaque psoriasis. The current study is a Phase IIb dose ranging study to assess the efficacy and safety of SCD-044 in the treatment of moderate to severe plaque psoriasis.

## 2. OBJECTIVES AND ESTIMANDS

### 2.1 Primary Objective

The primary objective of this study is to determine the effect of SCD-044 treatment on moderate to severe plaque psoriasis, as measured by proportion of subjects showing at least 75% improvement in Psoriasis Area and Severity Index (PASI) at Week 16.

### 2.2 Primary Estimand

The primary estimand is defined as follows:

Population of interest	Subjects with moderate to severe plaque psoriasis
Outcome Measure/Endpoint	Achieving at least 75% improvement in PASI at Week 16
Treatment	SCD-044 [REDACTED] and placebo once daily
Intercurrent Event	

Use of prohibited medications (as determined during blinded data review)

Early treatment discontinuation due to lack of efficacy, protocol deviation or AEs

 
Composite strategy will be applied to these intercurrent events and the subjects with intercurrent events will be treated as non-responders.

Population-level Summary Measure	Difference in proportions between each the active treatment arms and placebo arm

### 2.3 Secondary Objectives

The secondary objectives of this study are:

- To evaluate the efficacy of SCD-044 as measured by proportion of subjects achieving predefined improvement in Investigator's Global Assessment (IGA) of disease severity

- To evaluate the efficacy of SCD-044 as measured by proportion of subjects achieving predefined improvement in Psoriasis Area and Severity Index (PASI) and change in PASI scores over the treatment period
- To assess the effect of SCD-044 on the subject reported outcome measure of Psoriasis Symptoms and Signs Diary (PSSD)
- To assess the effect of SCD-044 on quality of life, as measured by Dermatology Life Quality Index (DLQI)
- To evaluate the efficacy of SCD-044 as measured by change in body surface area (BSA) involvement over the treatment period
- To assess the effect of SCD-044 on Patient Global Impression of Severity (PGIS)
- To assess the effect of SCD-044 on Patient Global Impression of Change (PGIC)
- To evaluate the PASI75 response in non-responders at low dose and intermediate dose when switched to high dose of SCD-044
- To assess the safety and tolerability of SCD-044 in subjects with moderate to severe plaque psoriasis
- [REDACTED]

## 2.4 Key Secondary Estimand

The key secondary estimand is defined similar to the primary estimand as follows:

Population of interest	Subjects with moderate to severe plaque psoriasis
Outcome Measure/Endpoint	Achieving an IGA of '0' or '1' with at least 2-grade reduction from baseline at Week 16
Treatment	SCD-044 [REDACTED] and placebo once daily
Intercurrent Event	

• Use of prohibited medications (as determined during blinded data review)

• Early treatment discontinuation due to lack of efficacy, protocol deviation or AEs.

 
Composite strategy will be applied to these intercurrent events and the subjects with intercurrent events will be treated as non-responders.

Population-level Summary Measure	Difference in proportions between each the active treatment arms and placebo arm

## 2.5 Tertiary Objectives

The tertiary objectives of this study are:

- To evaluate the efficacy of SCD-044 in the treatment of Scalp psoriasis as measured by Scalp IGA
- To evaluate the efficacy of SCD-044 in the treatment of nail psoriasis as measured by modified Nail Psoriasis Severity Index (mNAPSI) scores

- To evaluate the efficacy of SCD-044 in the treatment of psoriatic arthritis as measured by American College of Rheumatology (ACR) response
- To evaluate the efficacy of SCD-044 in the treatment of Palmoplantar Psoriasis as measured by Palmoplantar Physician Global Assessment (PPPGA) score

## 2.6 Exploratory Objectives

The exploratory objectives of this study are:

- [REDACTED]
- [REDACTED]
- [REDACTED]
- To evaluate the effect of SCD-044 on subject reported outcome of itching associated with Psoriasis
- To evaluate the effect of SCD-044 on Psoriatic Arthritis (PsA)-related Pain (Patient Assessment of Pain (PtAP))
- [REDACTED]

## 3. STUDY OVERVIEW

### 3.1 Study Design

Subjects in this randomized, double-blind, placebo controlled, parallel-group, multiple-center study will be assigned to treatment with the investigational products or placebo control according to a randomization scheme and [REDACTED] schedule.

- **Part I:** 16 weeks; Subjects will be randomized to placebo, Low dose ( [REDACTED] Intermediate dose ( [REDACTED] or High dose ( [REDACTED] of SCD-044 in [REDACTED] to assess primary and secondary endpoints at Week 16
- [REDACTED]  
[REDACTED]  
[REDACTED]  
[REDACTED]  
[REDACTED]  
[REDACTED]  
[REDACTED]

- [REDACTED]
- [REDACTED] response of [REDACTED] at Week 28 will
- [REDACTED]

[REDACTED]

Clinical Evaluations will be performed at:

- [REDACTED]
- [REDACTED]

Phone or in person contacts may be scheduled [REDACTED]

[REDACTED] to collect information on concomitant medication, compliance with the study drug use, health changes (AEs & AESI), queries for PML and PRES and to provide instructions.

[REDACTED]  
[REDACTED]

Subjects will be admitted into the study after informed consent has been obtained. An Unscheduled Visit is allowed at any time, for any reason, if in the Principal Investigator's opinion it is warranted. If a Subject is discontinued from the study during an Unscheduled Visit, the Unscheduled Visit will be referred to as an Early Discontinuation Visit and all procedures scheduled for Early Discontinuation will be performed. If the Unscheduled Visit is not an Early Discontinuation Visit (i.e., the Subject will continue to take part in the study), then all procedures scheduled for that Unscheduled Visit will be performed. Subjects who are discontinued early from the study must attend the Follow-up visit 4 weeks after the date of Early Discontinuation.

If necessary due to the coronavirus disease-2019 (COVID-19) pandemic, Visits 17, and 18 may have assessments done at home or remote visit. Remote visits must be discussed and

consulted with the Contract Research Organization's (CRO) and the Sponsor's Medical Monitor (MM) before planning. Scheduled blood collection (for these visits only) may be waived if the individual subjects have not had a clinically significant changes or undesired trend in lab or chemistry values prior to Visit 15. Subjects that have remote assessments or delayed Visits 17, or 18 will be recorded in the electronic case report form (eCRF) and noted as a minor protocol deviation.

COVID-19 related protocol deviations will be analyzed to assess whether a protocol amendment or other modifications are needed. The Sponsor together with investigators plan to assess the COVID-19 situation to evaluate the benefit: risk of the study on an ongoing basis.

Changes in study visit schedules, missed visits, or subject discontinuations may lead to missing information (e.g., for protocol-specified procedures). It is important to capture specific information in the subject records that explains the basis of the missing data, including the relationship to COVID-19, for missing protocol-specified information (e.g., from missed study visits or study discontinuations due to COVID-19).

A subset of eligible subjects will participate in photographic evaluation.

Randomization and re-randomization will be stratified by [REDACTED]  
[REDACTED]. Approximately, the same number of male and female subjects will be enrolled between treatment groups. [REDACTED]

[REDACTED]. Approximately, the same number of subjects who have prior exposure to biologics therapy for psoriasis will be enrolled between treatment groups.

The assigned Investigational Product will be administered orally once a day. Subjects will be required to use diaries to document the date of study treatments, any missed treatments and the occurrence of all adverse events.

The duration of each subject's participation in the study will be approximately 56 weeks (393 days).

If the Principal Investigator determines that the subject's condition has worsened to the degree that it is unsafe for the subject to continue in the study, the subject may be discontinued from the study as a treatment failure and the subject may be treated using the standard care.

Subjects with conditions or treatments that may affect cardiovascular safety (e.g., heart rate less than [REDACTED] history of uveitis or history of pulmonary conditions such as active severe respiratory disease (e.g., COPD, tuberculosis or pulmonary fibrosis, severe asthma or asthma requiring regular treatment with oral steroids) will be excluded due to the known mechanism-based AEs within this class which may expose such subjects to unwarranted excess risk for a condition with available alternatives.

[REDACTED]

### **3.3 Randomization and Unblinding Procedures**

In order to maintain the study blind, the randomization schedule will be generated by a third party. Randomization will be performed according to a computer-generated randomization scheme.

- [REDACTED]
- [REDACTED]
- [REDACTED]

-

- [REDACTED]

#### 4. STUDY ENDPOINTS/OUTCOMES

##### 4.1.1 Primary endpoint

The primary endpoint is the proportion of subjects with at least 75% improvement in PASI (PASI75) at Week 16.

##### 4.2 Key secondary endpoint

Key secondary endpoint of this study is the proportion of subjects achieving IGA of “clear” (0) or “almost clear” (1) with at least two-grade reduction from baseline to Week 16.

#### 4.3 Other secondary endpoints

The other (non-key) secondary endpoints of this study are:

- [REDACTED]
- [REDACTED]
- [REDACTED]
- Change from Baseline in PSSD score at Weeks 16, [REDACTED] and 52
- Change from Baseline in DLQI score at Weeks 16, [REDACTED] and 52
- Proportion of subjects with DLQI score of 0 or 1 at Weeks [REDACTED] 52.
- Proportion of subjects with IGA score of “clear” or “almost clear” with at least two-grade [REDACTED]
- [REDACTED]
- [REDACTED]
- Change from baseline in BSA involvement at Weeks [REDACTED] and 52
- Change from baseline in PGIS at Weeks [REDACTED] and 52
- Proportion of subjects with improvement in PGIC at Weeks [REDACTED] 52
- [REDACTED]
- Proportion of non-responders (<PASI75) at Week 16 in the low and intermediate dose groups who achieve a PASI75 response at Week [REDACTED] Week 52 after switch over to high dose
- [REDACTED]
- [REDACTED]
- Frequency, type, and severity of adverse events (AEs)

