4.2 Inclusion Criteria

1. Males and non-pregnant non-lactating females \geq 18 years of age providing written informed consent prior to any study-related procedures.
2. Diagnosis of predominantly plaque psoriasis for \geq 6 months as determined by subject interview and confirmation of diagnosis through physical examination by Investigator
3. Subject is a candidate for phototherapy or systemic therapy for plaque psoriasis.*
*Note: subjects are required to be candidates for systemic/phototherapy, however no such therapy will be allowed during the study. Please refer to exclusion criteria 3
4. Moderate to severe plaque psoriasis at Screening and Baseline defined as:
 - BSA involvement of \geq 10%
 - PASI score of \geq 12
 - IGA of at least moderate disease (\geq 3)
5. Negative evaluation for tuberculosis (TB) within 4 weeks prior to initiating IMP, defined as a negative QuantiFERON test. Subjects with a positive or 2 successive indeterminate QuantiFERON tests are allowed if they have all of the following:
 - No history of active TB or symptoms of TB
 - A posterior-anterior (PA) chest radiogram or chest computerized tomography (CT) Scan (with associated report available at the site) performed within 3 months of Screening with no evidence of active TB or of any other pulmonary infectious diseases)
 - If prior latent TB infection, must have history of adequate prophylaxis (per local standard of care)
 - If presence of latent TB is established, then treatment according to local country guidelines must have been followed for 4 weeks, prior to inclusion in the study. A maximum of 2 QuantiFERON tests are allowed. A re-test is only permitted if the first is indeterminate; the result of the second test will then be used.
6. Subjects must be in good health and free from any clinically significant disease, including but not limited to, known hypersensitivity to similar products or excipients, conditions that may interfere with the evaluation of plaque psoriasis. Such conditions include, but are not limited to atopic or contact dermatitis, eczema, tinea corporis, and psoriasis other than stable plaque psoriasis (e.g., erythrodermic, exfoliative or pustular psoriasis).
7. Willing to refrain from using all study prohibited medications during the treatment period.

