#### 4.4 Tertiary endpoints

Tertiary endpoints of this study are:

- Proportion of subjects with Scalp IGA “clear” or “almost clear” with at least two-grade reduction from baseline at Weeks [REDACTED] and 52 among subjects with a baseline Scalp IGA score of  $\geq 3$
- Proportion of subjects with nail psoriasis (baseline mNAPSI score of  $\geq 20$ ) who achieve at least a 75% improvement from baseline in total fingernail mNAPSI at Weeks [REDACTED] and 52
- Proportion of psoriatic arthritis subjects who achieve ACR20 response at Weeks [REDACTED] and 52
- Proportion of subjects with PPPGA score of 0 or 1 at Weeks [REDACTED] and 52 among subjects with a baseline PPPGA score of  $\geq 3$

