#### 4.5 Exploratory endpoints

Exploratory endpoints include:

- [REDACTED]
- [REDACTED]
- [REDACTED]
- Proportion of subjects achieving  $\geq$  4-point improvement in Itch Numeric Rating Scale (NRS) from baseline at Weeks [REDACTED], and 52 among subjects with a baseline Itch NRS of  $\geq$  4
- Proportion of subjects achieving  $\geq$  4-point improvement in Scalp Itch NRS from baseline at Weeks [REDACTED] and 52 among subjects with a baseline Scalp Itch NRS of  $\geq$  4
- Change from baseline in subject global assessment of PtA-P at Weeks [REDACTED] and 52 among subjects with PsA at baseline
- [REDACTED]

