### 5.2 Intent-to-Treat (ITT) Population

The Intent-to-Treat (ITT) Population will consist of all randomized subjects regardless of whether they received the investigational product. This population will be the main population for the efficacy analyses. Subjects will be analyzed according to the treatment they were randomized to receive.

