#### **6.8.3 Analysis of other endpoints**

All other endpoints will be summarized using the ITT population.

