#### **6.8.3.2 Binary endpoints**

Binary endpoints include:

- PASI50, PASI75, PASI90, PASI100 responses (i.e. reduction of at least 50%, 75%, 90% and 100% from baseline in PASI)
- IGA response (achieving IGA score of “clear” or “almost clear” with at least two-grade reduction from baseline)
- achieving PGIC improvement,
- Scalp IGA response (achieving Scalp IGA score of “clear” or “almost clear” with at least two-grade reduction from baseline).
- mNAPSI response (achieving at least a 75% improvement from baseline in total fingernail mNAPSI)
- ACR20 response (see the definition in the next section)
- achieving PPPGA score of 0 or 1
- achieving DLQI scores of 0 or 1
- achieving  $\geq$  4-point improvement in Itch NRS from baseline
- achieving  $\geq$  4-point improvement in Scalp Itch NRS from baseline.

Note that for all binary endpoints above that involve change from baseline or percent change from baseline, Part II baseline will be used for the groups that switch treatment in Part II, while Part I baseline will be used for the groups that stay on the same treatment throughout the study.

Number and percentage of subjects achieving these endpoints will be presented by treatment group along with 95% confidence interval for percentages based on binomial proportion.

Additionally shift tables will be created for IGA presenting shifts from baseline to post-baseline visits in Part I and Part II separately.

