### **8. CHANGES FROM PROTOCOL SPECIFIED ANALYSES**

Handling of intercurrent events is expanded in this SAP.

The endpoint of achieving DLQI score of 0 or 1 was added.

There are no other changes from the protocol-specified analyses.

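### The SAP-added endpoint of DLQI 0 or 1 has no baseline condition, so subjects who enter at 0 or 1 count as responders by staying there (low severity, cheap to fix)

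*SAP*

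**What the plan says.** SAP 4.3 lists "Proportion of subjects with DLQI score of 0 or 1 at Weeks", followed by a redaction and then 52. The redaction sits where week numbers belong, and the sentence ends at 52 with no qualifying clause. SAP 6.8.3.2 lists the same outcome for analysis as "achieving DLQI scores of 0 or 1". SAP 8 records that "The endpoint of achieving DLQI score of 0 or 1 was added", so no protocol definition stands behind it.

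The population comes from SAP 6.8.3: "All other endpoints will be summarized using the ITT population". Under SAP 5.2 that population "will consist of all randomized subjects regardless of whether they received the investigational product".

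Protocol 4.2, under "Moderate to severe plaque psoriasis at Screening and Baseline defined as", sets minimums for BSA (10%), PASI (12) and IGA (3). It sets none for DLQI.

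Other threshold endpoints in the SAP do carry a baseline clause. Scalp IGA is assessed "among subjects with a baseline Scalp IGA score of" 3 or more, and the itch endpoint "among subjects with a baseline Itch NRS of" 4 or more. PPPGA 0 or 1 (SAP 4.4) is limited to subjects with baseline PPPGA of 3 or more.

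For binary endpoints other than the primary and key secondary, SAP 6.8.3.2 plans the number, percentage and 95% confidence interval by treatment group. SAP 6.1.2 makes any other p-value nominal and rules out inference from it.

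**The concern.** A responder percentage on a state such as DLQI 0 or 1 will be read as the share of subjects brought to that state. The protocol's own DLQI table (6.1.1) labels 0–1 as having no effect on the patient's life. As defined, the percentage also includes anyone who was already there. That is possible at entry, because items marked not relevant score 0 and nothing in the eligibility criteria excludes a low total.

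Such subjects add roughly equal numbers of responders to every arm. They raise the placebo rate, shrink the difference from placebo and, through chance imbalance at baseline, add noise to it. The nearest analogue in the SAP, PPPGA 0 or 1, guards against this with a baseline floor.

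**Working it through.** **Is a floor supplied anywhere?** SAP 6.8.3.2 is not decisive alone, because its PPPGA entry also omits the floor that SAP 4.4 states. The defining text is SAP 4.3. In SAP 4.4 and 4.5 the baseline clause comes after the week list. In the DLQI line nothing comes after it. Neither SAP 6.8.3 nor the entry criteria fill the gap.

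**Stated figure.** The visible text gives no response rate, power or baseline distribution for DLQI 0 or 1, so there is nothing to reproduce. The one documented input is about 240 subjects allocated 1:1:1:1, which is 240/4 = 60 per arm.

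**Attenuation.** Let q be the share entering at 0 or 1, assumed to stay there in both arms. Let p0 and p1 be the response rates among the rest.

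- Observed rate = q + (1 − q)p
- Observed risk difference = (1 − q)(p1 − p0)

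All values of q, p0 and p1 below are assumptions. With p0 = 10% and p1 = 30%:

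| q | Expected at baseline 0/1 per arm of 60 | Placebo | Active | Difference (points) | Odds ratio |
|---|---|---|---|---|---|
| 0% | 0 | 10.0% | 30.0% | 20.0 | 3.86 |
| 2% | 1.2 | 11.8% | 31.4% | 19.6 | 3.42 |
| 5% | 3 | 14.5% | 33.5% | 19.0 | 2.97 |
| 10% | 6 | 19.0% | 37.0% | 18.0 | 2.50 |

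With 5% against 20%, the 15.0-point difference becomes 14.25 at q = 5% and 13.5 at q = 10%. The odds ratio moves more than the risk difference, but the SAP does not plan one for this endpoint.

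**Chance imbalance.** The standard deviation of the between-arm difference in baseline-0/1 share is √(2q(1 − q)/60).

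- q = 5%: √(2 × 0.05 × 0.95/60) = 4.0 points
- q = 10%: √(2 × 0.10 × 0.90/60) = 5.5 points

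An imbalance of d points moves the observed difference by about d(1 − p), so somewhat less than d.

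**How large might q be?** A beta-binomial DLQI on 0–30 with assumed moments gives 2.0% at 0 or 1 for mean 12, SD 6, and about 5–10% for mean 10, SD 6–7. With no treatment effect and a test-retest correlation of 0.70–0.85, the mean-10 scenarios give a Week 16 rate of 5.3–10.0%. That falls to 2.4–5.9% when baseline DLQI must be at least 2.

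**Which visits?** DLQI is collected at Weeks 0, 16, 20, 28 and 52 (protocol 6.1.1). Continuing placebo subjects are re-randomized to active drug at Week 16, so only Week 16 can provide a placebo contrast.

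**Switched groups.** SAP 6.8.3.2 applies the Part II baseline to switchers only for endpoints that involve change. DLQI 0 or 1 does not, and SAP 6.1 reads unqualified baseline as Part I. A placebo subject who reaches 0 or 1 by Week 16, moves to active drug and stays there would count as a responder under an active-dose label.

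**The case against.** The strongest reply is that this is an accurately labelled state measure on a non-key endpoint. Movement is captured separately by change from baseline in DLQI. The planned output is descriptive, any p-value is nominal, and at most one visit has a placebo arm. Subjects with PASI of at least 12, BSA of at least 10% and IGA of at least 3 who are candidates for systemic therapy or phototherapy may seldom score 0 or 1. All of this stands, and it keeps the severity low. It does not remove the definitional gap.

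Four stronger readings are tempting and are not supported:

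- **That every other threshold endpoint has a baseline floor.** ACR20 requires the CASPAR criteria but no minimum joint count. The itch floor of 4 is partly arithmetic, since a 4-point fall is impossible below 4. Scalp IGA and mNAPSI also require change. PPPGA 0 or 1 is the only close analogue.
- **That the endpoint loses power.** Power can be calculated under assumed rates, but it would describe a test that the SAP does not specify.
- **That as many as a fifth of subjects enter at 0 or 1.** A mean of 8 with SD 7 does give 20.3%, but in that distribution 0 is the most common baseline score (11.6%). That is hard to credit for this population, so it carries no weight here.
- **That a single-visit response is a defect.** The primary and key secondary endpoints are also assessed at one visit.

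The reply is also right that a floor of 2 is a partial remedy, because a one-point fall from 2 to 1 still counts.

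**Conclusion.** The point holds as a cheap improvement of low severity. Followed exactly, the plan counts a subject who enters and stays at DLQI 0 or 1 as a responder. For an assumed q of 2–10%, with those subjects staying at 0 or 1, a 20-point difference would read as 19.6 to 18.0 points, with some added chance noise. The size rests on q, which the documents do not give, and the contrast presumes that Week 16 is among the redacted weeks.

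A reader might infer bias in favour of the drug or a threat to the trial's main conclusions. Neither follows. Randomization balances these subjects in expectation, so the effect on the Week 16 contrast is attenuation and noise. The primary and key secondary tests do not use this endpoint.

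**What to change.** In SAP 4.3 and 6.8.3.2, define the endpoint as DLQI 0 or 1 among ITT subjects with Part I baseline DLQI of at least 2. State explicitly whether the Part I or Part II baseline defines the denominator for groups that switch treatment in Part II. A Part I floor alone does not remove subjects who reached 0 or 1 on their earlier treatment. Report the number with baseline DLQI 0 or 1 by arm. The unrestricted rate may stay as a footnote.

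No new data are needed, since DLQI is collected at Week 0. The cost is a short text change and a slightly smaller denominator: about 59, 57 or 54 of 60 per arm at q = 2%, 5% or 10%.

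The same edit should reconcile the DLQI scoring. SAP 6.8.3.1 gives the answer 'a little' 2 points, while protocol 6.1.1 gives it 1. Under the SAP values no item can score 1, so a total of 1 cannot occur and the endpoint reduces to DLQI 0.
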